Most patients with PCT have some degree of hepatic siderosis, but not marked iron overload (36). Therefore, only about 6-8 phlebotomies are needed to induce a remission in most cases. However, if the initial ferritin is markedly increased it can be predicted that more than the usual number of phlebotomies will be needed. As discussed above, many such individuals have hereditary hemochromatosis and are homozygous for the C282Y mutation of the *HFE* gene (especially among individuals of northern European origin) or are C282Y/H63D compound heterozygotes. Therefore it is important to measure serum ferritin, iron, and transferrin saturation, and to screen for the C282Y and H63D mutations in the *HFE* gene prior to starting phlebotomies. Infusions of deferoxamine, an iron chelator, or orally administered iron chelators, may be an alternative approach when phlebotomy is contraindicated, but are much less efficient for iron reduction (46, 47).

Advantages of phlebotomy can be summarized as follows:

- 1. Successful use for more than 50 years
- 2. Rationale is strong for treatment of an iron-related disease
- 3. Frequent visits facilitate monitoring of progress during treatment
- 4. Target laboratory value (ferritin) for completing therapy is well established

Disadvantages of phlebotomy include:

- 1. Expense
- 2. Discomfort, inconvenience and time requirements
- 3. Visits to clinic or blood bank required
- 4. Sometimes poorly tolerated (syncope, symptoms of iron deficiency, venous access problems, etc.)

Chloroquine and hydroxychloroquine. A low-dose regimen of these 4-aminoquinoline drugs is considered to be effective and a suitable alternative treatment when phlebotomy is contraindicated or difficult, and when there is not marked iron overload (48), as assessed by serum ferritin, liver biopsy or *HFE* mutations (particularly homozygosity for C282Y). This is the preferred therapy at some centers, especially for patients without marked iron overload (48, 49). These closely related drugs are interchangeable for this purpose, although hydroxychloroquine is considered to be safer in terms of retinal toxicity (50).

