The primary working hypothesis for this study is that time to remission with low-dose hydroxychloroquine is comparable to phlebotomy for treatment of PCT. Because of the very different features of the treatments, the study will be unblinded, but the major outcomes in terms of efficacy will be measurements that are objective. The study follows standard of care procedures for treating PCT, but assures that all participants have well-documented PCT, are characterized for multiple susceptibility factors, are assigned to treatment based on consistent criteria, and documents remission and recurrence of the disease, which are aspects often not accomplished in clinical practice.

The specific aims for testing the hypothesis are:

- Enroll up to 100 participants, including those enrolled to date, in a prospective, unblinded study comparing treatment by phlebotomy with treatment by low-dose hydroxychloroquine. Specified eligibility criteria will be used for treatment assignment and participants eligible for both treatments will be randomized, to avoid bias. Tolerability and safety of both treatments will be assessed by interviews and questionnaires.
- 2. Times to defined primary and secondary treatment outcomes will be compared and subjects will be followed for up to 5 years to assess durability of treatment.
- 3. Characterize all participants for the presence or absence of known susceptibility factors for PCT, including ethanol use, smoking, hepatitis C, HIV infection, estrogen use, HFE mutations and an inherited partial deficiency of UROD (as in familial, type 2 PCT), the latter as assessed by measuring erythrocyte UROD activity and DNA studies for UROD mutations. Some of these factors (e.g. heavy ethanol use, HFE mutations) will influence treatment assignment, and all will be used to determine if individual susceptibility traits influence treatment response and durability.

Use of hydroxychloroquine for treatment of PCT is an off label indication. The results of this study will contribute to future efforts to modify product labeling for hydroxychloroquine to include a specific dosing regimen for treatment of PCT.

4. Research design and methods

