The phlebotomy site must issue a report to document the date of each phlebotomy and the volume of blood removed, and provide a copy to the study site investigator. The information will be recorded in the CRF. If a scheduled phlebotomy is not done (e.g. hematocrit is below the permissible level), the reason should be recorded on the report to the site investigator. It must be determined in advance for each participant how documentation of each phlebotomy will be provided, as customary practices may vary among blood banks and other facilities that do therapeutic phlebotomies. Copies of this documentation will be retained at each site as source documents to verify each phlebotomy. Source documentation will need to be specified if phlebotomies are performed at other sites, such as CRCs and outpatient clinics. If such documentation is not received at the site, the coordinator will reach out to the outside facility to follow up appropriately. If an outside facility is being used for phlebotomies and does not provide documentation of the procedures, the participant will be given such a form to have completed by medical staff at the facility and will be responsible for sending this to the site

coordinator (see Appendix C). The cost of the phlebotomies will be considered standard of care and covered by the patient's insurance or by the Porphyrias Consortium if the patient has no insurance.

At each session, a hematocrit or hemoglobin determination will be done prior to the phlebotomy to assure this is high enough for tolerating phlebotomy. The permitted lowest value for each patient will be specified in advance and prerecorded, and will be no more than 10 points below the starting hematocrit, and no less than ~33. This value will be adjusted upward if there are concurrent medical conditions that need to be considered. The permitted hematocrit value is specified in advance to enhance safety and is not a therapeutic target.

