| Abbreviations: EOG = electro-oculogram; FAF = fundus autofluorescence; mfERG = multifocal electroretinogram; SD-OCT = spectral domain optical coherence tomography. | | | |

The recommendation in the product labeling for hydroxychloroquine for ophthalmological examination before and at 3 month intervals during treatment for lupus or rheumatoid arthritis is considered outdated and leads to unnecessary health care costs (50), and less frequent examinations are recommended in the recently revised guidelines of the American Academy of Ophthalmology (78).

Participants will be questioned at each visit about specific eye symptoms, such as reading and seeing difficulties, missing objects or parts of objects, missing or blacked out areas, blurred vision, halos around lights, photophobia, light flashes or streaks. Evidence of ophthalmic complications of hydroxychloroquine, although unlikely, will be reason for discontinuing the drug. The patient may then be treated by phlebotomy.

- V3 Date: 25FEB2020
- 4. Neuromuscular symptoms. Participants will be questioned at each visit regarding neuromuscular symptoms such as sensory changes and weakness, and examined for sensory changes, depression of deep tendon reflexes and loss of muscle strength, which are reported side effects of hydroxychloroguine.
- 5. Precautions for children. Participants taking hydroxychloroquine will be warned to keep the medication out of the reach of children.
- 6. Harmful exposures. Participants will be advised to avoid exposure to ultraviolet light (sunlight, tanning parlors, etc.) and alcohol, smoking, iron supplements, estrogens or other substances known to exacerbate PCT. This is part of standard clinical advice given to participants with PCT.
- **4.M. Efficacy.** Efficacy will be assessed primarily by laboratory results. Information on symptoms and signs will also be recorded.
 - 1. Laboratory Tests

The primary measures of efficacy will be plasma total porphyrin concentration, the plasma fluorescence emission spectrum at neutral pH, and urinary porphyrins (total as well as fractionated). The following will be measured at each visit.

- Plasma total porphyrins
- Plasma fluorescence emission spectrum at neutral pH
- Urinary porphyrins (total, and separation of individual porphyrins by high performance liquid chromatography-HPLC)
- Plasma and urinary exosomal ALAS1 mRNA

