4.O. Adverse experiences. At the time of each visit it will be determined whether any adverse experiences have occurred. The participants will be questioned in a general way and no specific adverse symptoms will be suggested, except in regard to the symptoms to be recorded on the CRFs or symptoms that are of particular importance in the clinical management of an individual patient. Any clinical adverse experiences that have occurred will be recorded on the CRFs, and a judgment made regarding whether or not the adverse experience was related to study treatment.

Any serious adverse experience (SAE), including death, due to any cause and occurring during the course of this investigation, whether or not related to the study treatments or procedures will be reported immediately to the Institutional Review Board (IRB) at the site, the IRB at UTMB, the Clinical Research Center at UTMB and the site, if required, and the US Food and Drug Administration.

A SAE with respect to clinical experience includes any experience that is fatal or life-threatening, is permanently disabling, or either requires or prolongs inpatient hospitalization.

4.P. Patient withdrawal. Every reasonable effort will be made to keep participants in the study. If a patient wishes to leave the study or is removed by the PI, a complete final evaluation will be performed. A narrative description of the reason(s) for withdrawal from the study will be recorded in the source documents.

The following are justifiable reasons for removing a patient from the study:

- 1. Development of a study exclusion criterion, as previously listed
- 2. If continuing the study presents an unacceptable risk or discomfort to the patient.
- 3. Violation of the study protocol.
- 4. The patient is uncooperative or noncompliant in study-related observations or in administration of study medication.
- 5. Consent is withdrawn.
- 6. The study is terminated.

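### Named symptom questions at each visit cover harms of hydroxychloroquine but, in the visible text, none of phlebotomy's, which could make phlebotomy look better tolerated

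*Combined protocol and SAP*

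**What the plan says.** **General rule.** Section 4.O sets how adverse experiences are asked about at each visit: "The participants will be questioned in a general way and no specific adverse symptoms will be suggested". The sentence continues with an exception: "except in regard to the symptoms to be recorded on the CRFs or symptoms that are of particular importance in the clinical management" for the participant concerned. Section 4.M (Cutaneous manifestations) adds that symptoms that might result from treatment go on the CRFs at each visit, but names none for phlebotomy.

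**Named questions.** Section 4.L, item 3: "Participants will be questioned at each visit about specific eye symptoms, such as reading and seeing difficulties", followed by further visual symptoms. Item 4: "Participants will be questioned at each visit regarding neuromuscular symptoms such as sensory changes and weakness", with an examination, on the stated ground that these are reported side effects of hydroxychloroquine.

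**Phlebotomy harms.** Section 2 lists among the disadvantages of phlebotomy: "Sometimes poorly tolerated (syncope, symptoms of iron deficiency, venous access problems, etc". Section 5.A adds pain, bruising and infection. Section 5.H.3 describes a sore, red vein, bruising and, rarely, fainting.

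**Phlebotomy records.** Section 4.F, Group 2: "The phlebotomy site must issue a report to document the date of each phlebotomy and the volume of blood removed". The reason is also to be given if a session is not done. Where an outside facility "does not provide documentation of the procedures, the participant will be given such a form" for its medical staff to complete. That form, Appendix C, has lines for side effects and venous access. A footnote to the Schedule of Events requires a phlebotomy visit sheet at every phlebotomy visit without stating its content.

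**Use of the data.** The synopsis lists tolerability and safety of both treatments among the outcome measures, and Section 3 says: "Tolerability and safety of both treatments will be assessed by interviews and questionnaires". Section 1.B asks whether hydroxychloroquine works as safely as phlebotomy, and 4.R plans a descriptive comparison of safety measures. Section 4.B says that comparing safety is not an objective.

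**The concern.** Symptoms asked about by name are generally reported more often than symptoms a patient must volunteer. If one treatment's characteristic harms are prompted at every visit and the other's are not, the two arms' counts are not on the same footing, and a descriptive table does nothing to correct that. The imbalance would favour phlebotomy.

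The protocol expects its results to guide the choice between the two treatments (1.B) and to contribute to future labeling of hydroxychloroquine (Section 3). The DSMB also reviews side effects as recorded on the CRFs (5.H). A tolerability difference produced by the way questions are asked would feed into all three.

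**Working it through.** The plan gives no tolerability event rate, capture rate or sample size to reproduce; the sample size in 4.R is for time to remission. The check is therefore mainly a comparison of the text.

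**1. Which named harms have a named question?**

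| Harm | Listed in | Named question at each visit (visible text) | Other visible route |
|---|---|---|---|
| Eye symptoms (hydroxychloroquine) | 5.A, 5.H.3 | Yes, 4.L item 3 | Eye examinations |
| Neuromuscular symptoms (hydroxychloroquine) | 4.L, 5.A, 5.H.3 | Yes, 4.L item 4 | Examination at each visit |
| Nausea, headache, dizziness and others (hydroxychloroquine) | 5.A, 5.H.3 | No | General question |
| Syncope (phlebotomy) | 2, 5.A, 5.H.3 | No | General question; Appendix C if used |
| Iron-deficiency symptoms (phlebotomy) | 2, 5.A | No | General question; ferritin, and hematocrit or hemoglobin |
| Venous-access problems (phlebotomy) | 2 | No | General question; Appendix C if used |
| Pain, bruising, infection (phlebotomy) | 5.A, partly 5.H.3 | No | General question; Appendix C if used |

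Every class with a named question is a hydroxychloroquine class. The pre-session blood test does not replace a question on iron deficiency, because 5.A says symptoms may occur without anemia.

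**2. Does the facility record close the gap?** A report of date and volume meets 4.F and can be silent about a faint. Appendix C would capture it, but 4.F describes handing out that form only where the facility supplies no documentation. The visit sheet might capture it, but its content is not given and it is not identified with Appendix C. The Appendix D chart records only that a phlebotomy took place.

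**3. Direction, and why the size cannot be fixed.** Suppose true incidence is equal in both arms. Let cp be capture when a symptom is asked by name and cu capture when it is not. Let s and t be the shares of hydroxychloroquine-arm and phlebotomy-arm events that fall in prompted classes. The ratio of observed incidences, hydroxychloroquine to phlebotomy, is

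R = [s·cp + (1 − s)·cu] / [t·cp + (1 − t)·cu].

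With cp above cu, R exceeds 1 whenever s exceeds t. With equal capture for all symptoms, R = 1.

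With t = 0, R runs from 1 (s = 0) to cp/cu (s = 1). The documents give none of the four quantities. Purely as assumptions, with cp = 90%, s = 1, t = 0 and a true incidence of 20% (observed hydroxychloroquine incidence 0.20 × 0.90 = 18%):

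| cu | Observed phlebotomy incidence | R = cp/cu |
|---|---|---|
| 70% | 0.20 × 0.70 = 14% | 1.29 |
| 50% | 0.20 × 0.50 = 10% | 1.80 |
| 30% | 0.20 × 0.30 = 6% | 3.00 |

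These are ceilings for each pair of capture rates, not estimates. Most hydroxychloroquine harms in 5.H.3 meet the same general question as phlebotomy harms, and 4.L does not expect ocular effects to be observed, so s may be well below 1. If the 4.L questions go to both arms, or the CRFs prompt for phlebotomy symptoms, t is above 0. Both pull R towards 1.

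**The case against.** The case against is substantial.

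- **CRF exception.** Sections 4.O and 4.M together allow treatment symptoms listed on the CRFs to be asked by name in either arm. The CRFs are not in the documents, so named phlebotomy items cannot be ruled out. In addition, the model phlebotomy order in 4.F breaks off after its third per-visit instruction in the available text. This stands as a limit on what can be concluded. It does not show that such prompts exist.
- **Both arms may be asked.** Items 3 and 4 of 4.L speak of participants, whereas item 5 and the eye-examination sentence specify those on hydroxychloroquine. If both arms are asked, capture of eye and neuromuscular symptoms is balanced. Phlebotomy's own harms still have no named question.
- **Other routes.** A visit sheet is due at each phlebotomy visit. Reasons for sessions not done, medical delays and changes of treatment are recorded, and 4.G plans contact every two weeks. These pick up intolerance that interrupts treatment, but not necessarily a faint or bruising after a completed session.
- **Schedule of Events.** It lists only alcohol and tobacco questionnaires and a PCT symptom assessment, with no tolerability questionnaire. It also has no row for adverse events or for the 4.L questions, so its silence shows nothing about asymmetry.
- **Safety is not the main objective.** Section 4.B says so, and 5.H puts the emphasis on time to remission. The synopsis, 1.B, Section 3 and 4.R point the other way. That conflict needs resolving and does not justify unequal elicitation.

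A reader might infer that the comparison is biased, that phlebotomy harms rest on unprompted recall alone, or that hydroxychloroquine's event rate would be inflated by a calculable factor. The documents support none of these. The relevant forms are not visible, and 4.R specifies no pooled event rate to which such a factor would apply.

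**Conclusion.** The point holds as a weakness of the visible text: the only symptoms that must be asked about by name at each visit are ones characteristic of hydroxychloroquine, and a phlebotomy report may satisfy the protocol without mentioning side effects. If the unseen forms do not correct this, phlebotomy could look better tolerated than it is. That direction rests on the assumption that prompting raises reporting. The size is unknown, and the ratios in the working only show how it depends on assumed capture rates. Because the comparison is descriptive and time to remission is unaffected, this is an inexpensive improvement and not a threat to the primary analysis.

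**What to change.** 1. **Section 4.O.** Use one solicited symptom checklist in both arms at every visit or telephone contact. It should cover the eye and neuromuscular symptoms of 4.L and the phlebotomy harms listed in Section 2, 5.A and 5.H.3. Keep the general question alongside it for everything else.
2. **Section 4.F and the Schedule of Events footnote.** Make the side-effects and venous-access items of Appendix C required for every phlebotomy wherever it is done, either on the phlebotomy visit sheet or obtained from the participant at the next contact. If the CRFs or visit sheet already contain such prompts, say so in the protocol.
3. **Section 4.R.** Tabulate solicited and unsolicited events separately by arm, and show participants enrolled before the change separately.
4. **Objectives.** Reconcile 4.B with the synopsis, 1.B, Section 3 and 4.R on whether safety and tolerability are compared.

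The cost is a short extra CRF page, a few minutes per contact and more mild events on record. The change cannot be applied retrospectively. Section 2 reports 52 participants enrolled at the originating site before the study became a consortium study, so a large part of the planned 100 will remain under the existing questioning.
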